6.1.9. TRC105 Study Drug Accountability

The Investigator must maintain an accurate accounting of TRC105 supplied by TRACON. During the study, the following information must be recorded:

- Date of receipt, quantity and lot number of the TRC105 study drug received from TRACON
- ID number of the patient to whom the product is dispensed
- The date(s) and quantity of the product dispensed
- Dates and quantity of product returned, lost or accidentally or deliberately destroyed

Investigational Drug Accountability Logs should be maintained by the site and must be readily available for inspection.

6.1.10. TRC105 Study Drug Handling and Disposal

TRC105 must be stored upright between 2 °C and 8 °C (36 °F to 46 °F). The Investigator should not return clinical study materials to TRACON unless specifically instructed to do so by TRACON. Used vials do not need to be maintained. All expired vials of TRC105 should be retained until destruction is authorized by a TRACON representative. The Site Pharmacist will be responsible for documenting the destruction (according to country-specific/institutional requirements) of used or expired vials.

6.2. Description of Axitinib

See axitinib package insert in [Section 20.3](#).

6.2.1. Composition of Axitinib

See axitinib package insert in [Section 20.3](#).

6.2.2. Axitinib Dose Level

Each patient will be dosed initially with 5 mg of axitinib twice per day for each day of a 28 day cycle. Dose de-escalation is permitted in cycle one and thereafter per the package insert.

6.2.3. Axitinib Packaging and Labeling

See axitinib package insert in [Section 20.3](#).

6.2.4. Axitinib Storage Handling and Disposal

See axitinib package insert in [Section 20.3](#).

6.2.5. Axitinib Dosing

Axitinib should be taken with or without food twice daily approximately 12 hours apart. On TRC105 dosing days, the morning axitinib dose should be taken at least 30 minutes prior to TRC105 dosing. The recommended dose is 5 mg axitinib taken orally twice each day of a 28-day cycle. Axitinib should be dosed at approximately the same times each day. Tablets shall be swallowed whole with a glass of water.

If the patient vomits or misses a dose (i.e., more than 6 hours elapses from the time of the usual dose), an additional dose should not be taken. The next prescribed dose should be taken at the usual time. Patients should not take more than two doses of axitinib on the same day. See axitinib package insert in [Section 20.3](#).

6.2.6. Axitinib Dose Modification

Patients who are intolerant of axitinib may continue TRC105 treatment alone on the study.

Axitinib should be held for two weeks prior and for two weeks following surgical procedures.

Dose reduction is allowed based on individual safety and tolerability. Following dose interruption, axitinib treatment may be reinitiated when the toxicity that prompted dose reduction has resolved to baseline or grade 1. See axitinib package insert in [Section 20.3](#).

All patients will initially receive axitinib 5 mg twice daily; patients randomized to receive TRC105 will receive TRC105 at 3 mg/kg on day 1, 7 mg/kg on day 4, and 10 mg/kg on day 8 and weekly thereafter. Patients **in both arms** who tolerate axitinib for at least two consecutive weeks with no adverse reactions > Grade 1 considered clinically significant (according to the Common Toxicity Criteria for Adverse Events [CTCAE]), will, at the discretion of their treating physician, have the axitinib dose increased to 7 mg twice daily beginning on cycle 2 day 1, unless the patient's blood pressure is > 150/90 or the patient is receiving more than one antihypertensive medication. Subsequently, with the same criteria, patients who tolerate the axitinib dose of 7 mg twice daily for at least two consecutive weeks may have the axitinib dose increased to a maximum of 10 mg twice daily beginning with cycle 3 day 1. Dose reductions of axitinib and TRC105 are allowed per patient tolerance (including to doses of axitinib between 5 and 10 mg twice daily). Reasons for dose reduction and reasons for not increasing the axitinib dose will be documented on the CRF.

Over the course of treatment, management of some adverse drug reactions may require temporary interruption or permanent discontinuation and/or dose reduction of axitinib therapy (including hypertension and hypertensive crisis, arterial and venous thromboembolic events, hemorrhage, gastrointestinal perforation and fistula formation, thyroid dysfunction, reversible posterior leukoencephalopathy syndrome, wound healing complications, proteinuria, and liver enzyme elevations). If dose reduction from 10 mg twice daily is required the recommended dose is 7 mg twice daily. If dose reduction from 7 mg twice daily is required, the recommended dose is 5 mg twice daily. If dose reduction from 5 mg twice daily is required, the recommended dose is 3 mg twice daily. If additional dose reduction is required, the recommended dose is 2 mg twice daily.

In the case of persistent hypertension despite use of anti-hypertensive medications, reduce the axitinib dose. Discontinue axitinib if hypertension is severe and persistent despite anti-hypertensive therapy and dose reduction of axitinib, and discontinuation should be considered if there is evidence of hypertensive crisis. If axitinib is interrupted, patients receiving antihypertensive medications should be monitored for hypotension.

Axitinib should be discontinued in patients who develop arterial thrombosis and the patient should be removed from study. Patients with grade 1 or 2 venous thromboembolism may dose reduce and continue treatment if it is the wish of the patient and physician and if the anticoagulation guidelines specified in [Section 6.3](#) are satisfied.

Axitinib should be interrupted for any bleeding requires medical intervention, gastrointestinal perforation, fistula, reversible posterior leukoencephalopathy syndrome, or surgical procedure. Interruption prior to and following surgery should be for a minimum of 2 weeks.

Thyroid function should be monitored before initiation of, and periodically throughout, treatment with axitinib. Treat hypothyroidism and hyperthyroidism according to standard medical practice to maintain a euthyroid state.

The dose of axitinib should be temporarily interrupted and/or reduced for patients who develop grade 3 or 4 proteinuria or grade 3 or 4 transaminase or bilirubin elevations.

Patients assigned to the combination arm who cannot tolerate axitinib therapy and who demonstrate a response of complete response (CR), partial response (PR) or stable disease (SD) with the combination and are thought to benefit from continued TRC105 therapy may continue on study on TRC105 alone.

Table 17: Ideal Axitinib Dose Escalation Schedule

Axitinib Available Dose Levels	Cycle Day
5 mg BID	Cycle 1 Day 1 to Cycle 2 Day 1
7 mg BID	Cycle 2 Day 1 to Cycle 3 Day 1
10 mg BID	Cycle 3 Day 1+

6.2.7. Axitinib Drug Accountability

Patients will be asked to bring their axitinib bottle/blister packs to the clinic at the beginning of each cycle for proper drug accountability. Additional axitinib should be dispensed as needed. Upon patient discontinuation, unused axitinib tablets should be destroyed according to country-specific regulations/institution guidelines. Please see study specific pharmacy binder for detailed information regarding axitinib dispensing and accountability.

6.3. Concomitant Medications

No other approved or investigational anticancer treatment will be permitted during the study period. No other investigational drug may be used during treatment on this protocol, and concurrent participation in another clinical trial is not allowed.

Patients who receive NSAIDs on study for more than three consecutive days should also receive peptic ulcer disease (PUD) prophylaxis with an H2 or proton pump blocker.

Narcotic analgesics, nonsteroidal anti-inflammatory drugs, and triptans (e.g. sumatriptan) may be offered as needed for relief of pain or headaches. Triptans are recommended for patients who experience a migraine headache following dosing, and may be taken prior to the occurrence of headache, as a prophylactic medication. Antihistamines and decongestants may be offered for the treatment of sinus congestion.

Packed red blood cell, colony stimulating factors, and platelet transfusions should be administered as clinically indicated.

Concomitant use of strong CYP3A4/5 inhibitors should be avoided (Table 18). Patients may not have received a strong CYP3A4/5 inducer within 12 days prior to registration nor a strong CYP3A4 inhibitor within 7 days prior to registration. Selection of an alternate concomitant medication with no or minimal CYP3A4/5 inhibition potential is recommended. Grapefruit or grapefruit juice may also increase axitinib plasma concentrations and should be avoided.

Although axitinib dose adjustment has not been studied in patients receiving strong CYP3A4/5 inhibitors, if a strong CYP3A4/5 inhibitor must be co-administered, a dose decrease of axitinib by approximately half is recommended, as this dose reduction is predicted to adjust the axitinib area under the plasma concentration versus time curve (AUC) to the range observed without inhibitors. The subsequent doses can be increased or decreased based on individual safety and

tolerability. If co-administration of the strong inhibitor is discontinued, the axitinib dose should be returned (after 3 – 5 half-lives of the inhibitor) to that used prior to initiation of the strong CYP3A4/5 inhibitor.

Co-administration of rifampin, a strong inducer of CYP3A4/5, reduced the plasma exposure of axitinib in healthy volunteers. Co-administration of axitinib with strong CYP3A4/5 inducers (e.g., rifampin, dexamethasone, phenytoin, carbamazepine, rifabutin, rifapentin, phenobarbital, and St. John's wort) should be avoided. Selection of concomitant medication with no or minimal CYP3A4/5 induction potential is recommended. Moderate CYP3A4/5 inducers (e.g., bosentan, efavirenz, etravirine, modafinil, and nafcillin) may also reduce the plasma exposure of axitinib and should be avoided if possible.

Table 18: Strong CYP3A4/5 Inducers and Inhibitors

Inducers:	^aInhibitors:	
dexamethasone	Boceprevir	Conivaptan
phenytoin	Indinavir	Itraconazole
carbamazepine	Nelfinavir	Ketoconazole
rifampin	Lopinavir/ritonavir	Mibefradil
rifabutin	Saquinavir	Nefazodone
rifapentin	Telaprevir	Posaconazole
phenobarbital	Ritonavir	Voriconazole
St. John's Wort	Clarithromycin	Telithromycin

^a Because the lists of these agents are constantly changing, it is important to regularly consult a comprehensive list such as the one located at <http://medicine.iupui.edu/clinpharm/ddis/>.

Patients with arterial thrombosis or grade 3 or 4 venous thrombosis should be removed from study. Patients with grade 1 or 2 venous thrombosis who require anticoagulation will have their TRC105 therapy interrupted. TRC105 therapy may resume once the following criteria are met:

- The patient is on a stable dose of heparin or low molecular weight heparin or Factor X inhibitor.
- The patient has a platelet count > 100,000.
- The patient has not had a hemorrhagic event of grade 2 or higher while on study.
- The patient does not have a pathological condition that carries a high risk of bleeding (e.g., tumor involving major vessels).
- The patient is benefiting from TRC105 therapy (no evidence of disease progression).

6.4. Treatment Compliance

6.4.1. TRC105 Treatment Compliance

All TRC105 infusions will occur at the trial site under the direct supervision of the treating physician or his or her designee.

6.4.2. Axitinib Treatment Compliance

Patients will be asked to record the day and time of axitinib home dosing on a TRACON supplied log to be reviewed by site personnel prior to initiation of each new cycle.

6.5. Patient Enrollment

Patients will be manually enrolled by TRACON Pharmaceuticals and assigned an eight digit patient number. This eight digit number will be used to identify patients throughout their participation in the trial. For the phase 2 portion of the study patients will also be assigned to Arm A (axitinib therapy alone) or Arm B (TRC105 + axitinib). A regulatory binder will be provided and will include detailed instructions for the manual enrollment process.

7. ASSESSMENT OF EFFICACY

7.1. Radiological Tumor Assessment

The primary efficacy assessment will be best overall response by RECIST 1.1 in Phase 1b and in phase 2 as defined in [Section 7.1.2](#). The determination of antitumor efficacy will be based on objective tumor assessments made by Central Radiographic Review according to RECIST version 1.1 and Choi criteria [66]. However, Investigators will make treatment decisions using RECIST 1.1 based on their own review. All lesions will be classified as target or non-target lesions at the Screening visit. Each lesion designation will be maintained through the course of the study.

Subjects should receive CT or MRI scans of chest, abdomen, and pelvis with contrast. If subjects are unable to receive CT contrast due to CT contrast medium allergy or renal insufficiency, enhanced MRI scans may be used. A combination of non-contrast CT and MRI studies (such as chest CT without contrast and abdominal MRI with contrast) may be used. The same method of assessment must be used throughout the course of the study thereafter.

Similarly, if a subject develops a contraindication to CT contrast during the course of the study; assessments may shift to non-contrast CT of the chest and contrast-enhanced MRI of the abdomen for subsequent scans. Such a situation does not imply mandatorily a NE overall response.

The same method and technique should be used to characterize each identified and reported lesion at Screening, during the study treatment period, and at the End of Study visit. Imaging-based evaluation over clinical examination is the required technique when both could be used to assess the antitumor effect of the treatment. Clinical Oncology review of all tumor measurements is desired.

Whenever possible, clinical evaluation of superficial lesions should not be used as the sole form of measurement. However, when necessary, color photograph with metric caliber is acceptable. Tumor evaluation by positron emission tomography (PET) scan or by ultrasound may not substitute for CT or MRI scans.

Radiological tumor assessments will be performed at screening, as outlined in the Schedule of Assessments ([Table 7](#), [Table 8](#), [Table 9](#), [Table 10](#), and [Table 11](#)), and whenever disease progression is suspected. Another tumor assessment will be performed at the End of Study Visit if an assessment has not been performed within the prior 8 weeks. All patient files and radiological images must be available for CRF source verification.

7.1.1. Measurability of Tumor Lesions

At Screening, individual tumor lesions will be categorized by the Investigator as either target or non-target according to RECIST 1.1 as described below.

- **Measurable:** Lesions that can be accurately measured in at least one dimension (longest diameter to be recorded) as ≥ 10 mm with spiral CT scan. Lytic bone lesions, with an *identifiable soft tissue component*, evaluated by CT or MRI, *can be considered as measurable lesions* if the soft tissue component otherwise meets the definition of measurability previously described. Blastic bone lesions are non-measurable. Lesions in

previously irradiated areas (or areas treated with local therapy) should not be selected as target lesions, unless there has been demonstrated progression in the lesion. Clinical lesions will only be considered measurable when they are superficial (e.g. skin nodules, palpable lymph nodes) and ≥ 10 mm. Clinical lesions must be measured with calipers.

- **Non-Measurable:** All other lesions, including small lesions and bone lesions other than lytic bone lesions, leptomeningeal disease, ascites, pleural or pericardial effusions, lymphangitis of the skin or lung, abdominal masses that are not confirmed and followed by imaging techniques, previously irradiated lesions (unless there has been demonstrated progression in the lesion), and disease documented by indirect evidence only (e.g. by laboratory tests such as alkaline phosphatase).

7.1.1.1. Recording Tumor Measurements

Measurable lesions up to a maximum of 5 lesions representative of all involved organs (with a maximum of 2 lesions per organ) should be identified as target lesions and measured and recorded at Screening and at the stipulated intervals during treatment. Target lesions should be selected on the basis of their size (lesion with the longest diameters) and their suitability for accurate repetitive measurements (either by imaging techniques or clinically). Target lesions may include lymph nodes with a short axis ≥ 15 mm.

The longest diameter will be recorded for each target lesion (with the exception of lymph nodes, where the short axis will be used). The sum of the diameter for all target lesions at Screening will be calculated and recorded as the baseline sum diameter to be used as reference to further characterize the objective tumor response of the measurable dimension of the disease during treatment. All measurements should be performed using a caliper or ruler and should be recorded in metric notation in millimeters.

All other lesions (or sites of disease) should be identified as non-target lesions and should also be recorded at baseline. Measurements are not required and these lesions should be followed as “present”, “stable”, “absent”, “increased” or “decreased”.

7.1.2. Definitions of Tumor Response

7.1.2.1. Target Lesions

- **Complete response (CR)** is defined as the disappearance of all target lesions.
- **Partial response (PR)** is defined as a $\geq 30\%$ decrease in the sum of the dimensions of the target lesions taking as a reference the baseline sum dimensions.
- **Progressive disease (PD)** is defined as a $\geq 20\%$ relative increase and ≥ 5 mm absolute increase in the sum of the dimensions of the target lesions taking as a reference the smallest sum of the dimensions recorded since the treatment started, or the appearance of one or more new lesions.
- **Stable disease (SD)** is defined as neither sufficient shrinkage to qualify for PR nor sufficient increase to qualify for PD taking as a reference the smallest sum of the dimensions since the treatment started.

7.1.2.2. Non-Target Lesions

- **Complete response (CR)** is defined as the disappearance of all non-target lesions.
- **non-CR/non-PD** is defined as a persistence of ≥ 1 non-target lesions.
- **Progressive disease (PD)** is defined as unequivocal progression of existing non-target lesions, or the appearance of ≥ 1 new lesions.

The cytological confirmation of the neoplastic origin of any effusion that appears or worsens during treatment when the measurable tumor has met criteria for response or stable disease is mandatory to differentiate between response or stable disease and progressive disease.

7.1.3. Determination of Overall Response

7.1.3.1. Determination of Overall Response by RECIST 1.1

When both target and non-target lesions are present, individual assessments will be recorded separately. The overall assessment of response will involve all parameters as depicted in Table 19 below. Per RECIST 1.1, as the phase 1b portion is non-randomized and with response is a primary endpoint, confirmation of PR or CR is required. However, for the phase 2 portion, since the phase 2 portion is randomized, confirmation of response will not be required. Per RECIST 1.1, a modest increase in the size of one or more non-target lesions is usually not sufficient to qualify for unequivocal progression status.

Table 19: Response Evaluation Criteria in Solid Tumors

Target Lesions ^a	Non-target Lesions ^b	New Lesions ^c	Overall Response
CR	CR	No	CR
CR	non-CR/non-PD	No	PR
CR	Not evaluated	No	PR
PR	Non-PD or not all evaluated	No	PR
SD	Non-PD or not all evaluated	No	SD
Not all evaluated	Any Response	Yes or No	Not Evaluable
PD	Any Response	Yes or No	PD
Any Response	PD	Yes or No	PD
Any Response	Any Response	Yes	PD

^aMeasurable lesions only.

^bMay include measurable lesions not followed as target lesions or non-measurable lesions.

^cMeasurable or nonmeasurable lesions.

The best overall response is the best response recorded from the start of the treatment until disease progression/recurrence (taking as reference for progressive disease the smallest

measurements recorded since the treatment started). The patient's best response assignment will depend on the achievement of both measurement and confirmation criteria.

NOTE: Patients with a global deterioration of health status requiring discontinuation of treatment without objective evidence of disease progression at that time should be reported as "Need for additional anti-cancer therapy/surgery". Every effort should be made to document the objective progression even after discontinuation of treatment.

In some circumstances, it may be difficult to distinguish residual disease from normal tissue. When the evaluation of complete response depends upon this determination, it is recommended that the residual lesion be investigated by fine needle aspirate or biopsy before confirming the complete response status.

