10.5. Analysis of Primary and Secondary Objectives

10.5.1. Phase 1b

For each cohort, DLTs will be summarized by category (hematologic and non-hematologic) and by MedDRA preferred term.

All AEs with an onset after initiation of treatment will be considered as treatment-emergent AEs. A preexisting condition that worsens during the treatment period will also be considered as a treatment emergent AE. All AEs will be coded by system organ class (SOC) and preferred term using NCI CTCAE (MedDRA) version 4.0.

The number and percentage of patients with the following types of treatment-emergent AEs will be summarized: common and serious AEs, AEs related to study medication, AEs resulting in study discontinuation, and clinically significant laboratory abnormalities. Non-treatment-emergent serious AEs will be described separately. Deaths will be reported with demographic information.

10.5.2. Phase 2

The primary endpoint for efficacy will be PFS, defined as time from randomization to either first disease progression (per independent radiology review of images by RECIST) or death from any cause. PFS will be censored on the day following the date of the last tumor assessment documenting absence of progressive disease for patients who do not have objective tumor progression and are still on study at the time of analysis, are given antitumor treatment other than the study treatment, are removed from study follow-up prior to documentation of objective tumor progression, died of non-cancer causes including death due to an unknown cause in the absence of documented disease progression.

The PFS distributions in the two arms will be summarized using the Kaplan-Meier method. The distributions will be compared using a stratified (by performance status) log-rank test at the one-sided $\alpha=0.10$ level of significance.

Additional exploratory analyses of PFS will be conducted in subgroups defined based on number of prior therapies (one, two or three). The same methods as for the primary analysis (Kaplan-Meier survival estimation, log rank tests) will be used. The effects of these covariates may also be assessed using Cox proportional hazards regression models.

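### Table 19 grades a visit with incompletely evaluated target lesions and a new lesion or non-target progression as both Not Evaluable and PD, with no rule of precedence

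*Protocol*

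**What the plan says.** Protocol Section 7.1.3.1 makes Table 19 the governing rule: "The overall assessment of response will involve all parameters as depicted in Table 19 below". Three of its rows matter here, the first of them for target lesions that are "not all evaluated". The columns, in order, are target lesions, non-target lesions, new lesions and overall response:

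- "Not all evaluated Any Response Yes or No Not Evaluable"
- "Any Response PD Yes or No PD"
- "Any Response Any Response Yes PD"

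The lesion-level definitions agree with the last two rows. Section 7.1.2.1 counts as target-level PD a sufficient increase in the sum of dimensions, "or the appearance of one or more new lesions". Section 7.1.2.2 defines non-target PD as "unequivocal progression of existing non-target lesions, or the appearance of ≥ 1 new lesions".

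The primary phase 2 endpoint depends on these grades. Protocol Section 10.5.2 defines PFS as time from randomization to "first disease progression (per independent radiology review of images by RECIST) or death from any cause". SAP Section 11.1 bases primary PFS on central review by RECIST 1.1. The SAP neither reproduces nor corrects Table 19.

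**The concern.** A visit at which some target lesions were not assessed, but a new lesion or non-target progression was seen, meets the Not Evaluable row and at least one PD row. The table gives no order of precedence, so two readers who both follow it can reach different grades for the same images. One grade is a PFS event and the other is not.

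Such visits are foreseeable. Protocol Section 4.1.2.2 calls for imaging when progression is suspected and for on-study brain imaging if brain metastases are suspected. A symptom-driven brain scan that shows a new metastasis, without repeat body imaging, leaves the target set incomplete.

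If central review grades such a visit Not Evaluable, two things can follow:

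- **Delay.** The patient stays on study and progression is dated at the next scan that can be graded.
- **Loss.** The investigator, who decides treatment on his or her own reading (Protocol Section 7.1), calls progression and treatment ends. The end-of-study scan can be omitted if one was done in the preceding 8 weeks (Section 4.1.3), and post-treatment follow-up (Section 4.1.4) lists no imaging. SAP Section 11.1 then censors at the last assessment before new antitumor therapy, or at the last assessment on study. Its rule of censoring when central and investigator assessments conflict could also be triggered.

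SAP Section 4.2 lets the sponsor run the final analysis with fewer than 115 events, so a lost event need not be replaced.

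**Working it through.** **1. Table 19 as a lookup.** Fix the target column at incompletely evaluated, cross each non-target state with new lesion yes or no, and list every row that applies.

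| Non-target | New lesion: yes | New lesion: no |
|---|---|---|
| CR | Not Evaluable and PD | Not Evaluable |
| Non-CR/non-PD | Not Evaluable and PD | Not Evaluable |
| Not evaluated | Not Evaluable and PD | Not Evaluable |
| PD | Not Evaluable and PD (two PD rows) | Not Evaluable and PD |

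Five of the eight combinations return both grades. Only the three with no new lesion and no non-target PD return one.

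**2. Does a narrower reading remove the conflict?** Suppose an incompletely evaluated target set is not a response at all, so that rows accepting any target response do not cover it. The Not Evaluable row then governs alone, and its new-lesion cell expressly includes yes. A new lesion would be Not Evaluable in Table 19 and PD in Sections 7.1.2.1 and 7.1.2.2. The conflict moves but remains.

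**3. The plan's event count.** Inputs from Protocol Section 10.2.1: HR 0.67, one-sided alpha 0.10, power 80%, 1:1 allocation, 115 events. With z(0.90) = 1.2816 and z(0.80) = 0.8416, the squared sum is 4.508.

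- Schoenfeld: 4 × 4.508 / (ln 0.67)² = 112.4, so 113 events.
- Freedman: 4.508 × (1.67/0.33)² = 115.4, so 116 events.

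The stated 115 lies between them and is reproduced.

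**4. Power if events are permanently lost.** Power = Φ(½ √d × |ln 0.67| − 1.2816), with |ln 0.67| = 0.4005. The documents give no frequency for these visits, so the loss is an assumption. Three to five percent of 115 is 3.45 to 5.75, or about 3 to 6 events.

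| Events counted | Assumed loss | Power |
|---|---|---|
| 115 | none | 80.7% |
| 112 | 3 events (about 3%) | 79.9% |
| 109 | 6 events (about 5%) | 79.1% |
| 103.5 | 10% | 77.5% |
| 97.8 | 15% | 75.8% |

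The last two rows show sensitivity only. Every row after the first assumes that each affected visit is read as Not Evaluable and that its event is never recovered.

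**5. Size of a delay.** Phase 2 scans are 56 days apart (window ± 7 days). 56 / 30.4375 = 1.84 months, and 1.84 / 4.8 = 38% of the control median PFS assumed in Section 10.2.1. This is a nominal upper figure for a delay of one scan interval. An unscheduled scan shortens it.

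**The case against.** The strongest reply is that the protocol already points to PD. Both lesion-level definitions make a new lesion PD, so a new-lesion visit satisfies three PD rows of Table 19 against one Not Evaluable row. A trained central reader would probably grade it PD, and the central-review charter, which is not among the documents, may say so. That makes the Not Evaluable reading less likely. It does not repair a table that the protocol names as governing and that prints the opposite answer.

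A reader might infer that every affected patient loses an event or has it delayed by at least 56 days. The documents do not support that. Nothing happens unless the Not Evaluable row is applied, imaging is required on suspicion of progression and so may come sooner than the next scheduled scan, and death from any cause remains a PFS event.

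A reader might also infer a biased treatment comparison. Censoring prompted by a real new lesion is informative, but nothing in the documents shows that such visits would be more common in one arm.

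It is also fair to say that the SAP's censoring rules operate whatever Table 19 says, and that a delayed event is still an event. If the sponsor waits for 115 events, the power figures for lost events do not apply. The permission in SAP Section 4.2 to analyze earlier is why loss cannot be dismissed.

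**Conclusion.** Wrong as written. Table 19 gives two overall responses to an incompletely evaluated visit with a new lesion or non-target PD, and no precedence rule resolves it. This is certain from the text and depends on no assumed frequency.

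The consequence is conditional on central review applying the Not Evaluable row. A progression would then be misdated, nominally by up to 56 days, or lost to censoring. The numerical effect is probably small: 0.8 to 1.6 points of power if 3–5% of events were permanently lost, a frequency that is assumed. If the analysis waits for 115 events, the cost is mainly misdating and delay. The case for correction is that a rule defining the primary endpoint should give one answer per visit, not that the trial's power is in doubt.

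**What to change.** Rewrite the Not Evaluable row of Table 19 as follows:

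- target lesions: incompletely evaluated (label unchanged);
- non-target lesions: non-PD or "not all evaluated";
- new lesions: No;
- overall response: Not Evaluable.

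The non-target cell needs both alternatives. The PR and SD rows of Table 19 treat them as separate states, so non-PD alone would leave no row for a visit at which both target and non-target lesions were incompletely evaluated and no new lesion was seen. A sentence giving the PD rows precedence would serve equally well. Under either change the five conflicting combinations return PD only, and the other three remain Not Evaluable.

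Carry the same table into the SAP and the central-review instructions. While SAP Section 11.1 is open, state whether a Not Evaluable visit counts as a missed assessment under its rule for consecutive missing assessments, which is not defined.

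The cost is one table row and its copies. The 115-event target is unchanged, and no dose or treatment rule is affected.
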